### **2.6.2 Statistical hypothesis, model, and method of analysis**

No formal statistical tests will be performed for any of the secondary efficacy endpoints and hence no multiplicity adjustment will be applied.

Time-to-event endpoints will be analyzed using Kaplan-Meier method: the Kaplan-Meier curves, medians and 95% CI of the medians will be presented.

### **2.6.3 Handling of missing values/censoring/discontinuations**

The censoring rules for time to event endpoints are described in the definitions above.

## **2.7 Safety analyses**

Safety analyses will be summarized for the safety set and by dose level of MBG453 (400 mg Q4W, 800 mg Q4W) and for all subjects (“All subjects” column).

Safety summaries (tables, figures) include only data from the on-treatment period with the exception of baseline data which will also be summarized where appropriate (e.g. change from baseline summaries). In addition, a separate summary for death including on treatment and post treatment deaths will be provided. In particular, summary tables for adverse events (AEs) will summarize only on-treatment events, with a start date during the on-treatment period (treatment-emergent AEs).

The overall observation period will be divided into three mutually exclusive segments:

1. Pre-treatment period: from day of subject’s informed consent to the day before first administration of study treatment
2. On-treatment period: from date of first administration of study treatment to 30 days after date of last administration of study treatment
3. Post-treatment period: any observation starting at day 31 after last administration of study treatment

An overall safety period will be defined from date of first administration of study treatment to 150 days after the last dose of MBG453.

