	Subsequent occurrences in next treatment cycles after achieving remission (CR, CRi, MLFS) and lasting at least 7 days	Delay subsequent treatment and monitor blood counts. Administer G-CSF if clinically indicated for neutropenia. Once the toxicity has resolved to Grade 1 or 2, resume venetoclax therapy at the same dose with a duration reduced by 7 days for each subsequent treatment cycle
Blood chemistry changes suggestive of TLS	-	Withhold treatment. If the event is resolved within 48 hours of last dose, treatment with venetoclax can be resumed at the same dose.

Event	Occurrence	Action
Events of clinical TLS or blood chemistry changes requiring more than 48 hours to resolve	-	Withhold treatment. Treatment should be resumed at a reduced dose (per the investigator discretion). When resuming treatment after interruption due to TLS, the instructions for prevention of TLS should be followed.
Grade 3 or 4 non-hematologic toxicities	First occurrence	Withhold treatment. Once the toxicity has resolved to Grade 1 or baseline level, venetoclax therapy may be resumed at the same dose.
	Subsequent occurrences	Withhold treatment. Treatment should be resumed at a reduced dose (per the investigator discretion).

Permanent discontinuation of study treatment

If the study treatment (i.e. MBG453 + azacitidine + venetoclax) is interrupted for toxicities and the start of the subsequent study treatment cycle is delayed for more than 42 consecutive days (measured from the intended start date of the new cycle (Day 29 of the previous cycle) in absence of clinical benefit for the patient per investigator assessment, the subject should be discontinued from study treatment.

At any time during the study, patients unable to tolerate one or two of the study treatment drugs may continue study treatment with only the tolerated drug(s) provided the subject benefits per investigator's judgement.

These dose changes must be recorded on the appropriate CRF.

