9.1.1.1 Safety Follow-up

All patients must be followed for safety for 150 days after the last dose of MBG453 or 30 days after the last dose of azacitidine or venetoclax whichever is longer.

After the 30-Day on-site safety follow-up visit, patients will be followed via telephone call (or on-site visit if patient happens to be visiting the site) at 90 and 150 days after the last dose of MBG453. All safety assessments should be completed as per [Table 8-1](#). However, if the patient begins new antineoplastic medication before the end of the safety follow-up period, the collection of new SAEs and AEs unrelated to study medication will stop and thereafter only suspected AEs and suspected SAEs will continue to be collected up to the end of the safety follow-up period. Patients continuing on MBG453 through an alternative setting (e.g. managed access program or a roll-over study) after the end of the study, should be followed for safety until the EOT visit. For female patients of child bearing potential, a pregnancy test will be performed at the timepoints listed in [Table 8-1](#)

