## **Full Analysis Set**

The Full Analysis Set (FAS) comprises all subjects who received at least one dose of any component of the study treatment (i.e. at least one dose of MBG453 or at least one dose of azacitidine or at least one dose of venetoclax).

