## **Dose-Determining Set**

The Dose-Determining Set (DDS) includes all subjects from the FAS enrolled in the safety run-in part who met the minimum exposure criterion and had sufficient safety evaluations, or experienced a dose limiting toxicity (DLT) starting from Cycle 1 Day 8 to the end of Cycle 2. Details on the definition of dose limiting toxicities (DLT) are presented in [Table 2-2](#). A subject will be considered evaluable for DLT if:

- Subject has received 2 infusions of MBG453 at the assigned dose level in Q4W dosing regimen, and has taken at least 75 % of the planned dose of azacitidine and venetoclax (i.e. for 2 cycles: 11 doses of azacitidine out of the 14 doses planned and 42 doses of venetoclax out of the 56 doses planned with a successful ramp up to full dose where full dose is equal to 400 mg or less when administered concomitantly with CYP3A4 inhibitors or P-gp inhibitors), and subject has had safety assessments for a minimum period of 2 cycles (from Cycle 1 Day 1 to the end of Cycle 2), or
- Subject has experienced a DLT within the DLT observation period from first dose of MBG453 to the end of Cycle 2. Note that subjects who experience toxicity that meets the criteria for DLT but occurs prior to the first dose of MBG453 will be considered not evaluable.

Note: A subject who leaves the study before receiving any dose of MBG453 will not be included in the DDS.

Note: For a subject with a grade 4 neutropenia, thrombocytopenia and pancytopenia (hematological toxicity that could be qualified as a DLT) occurred during the DLT evaluation period (from Cycle 1 Day 8 to the end of Cycle 2), a sufficient follow-up time will be considered to determine if the adverse event has to be qualified as a DLT. As per protocol, only persistent grade 4 neutropenia, thrombocytopenia and pancytopenia beyond Day 42 from the start of a study treatment cycle and is not related to leukemic infiltration will be considered to be a DLT (bone marrow evaluation may be required to determine if marrow aplasia is due to leukemia). Thus, in such a situation, the cut-off date for the safety review meeting could be delayed to enable to qualify or not this hematological toxicity as a DLT.

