### **2.7.1 Adverse events (AEs)**

Summary tables for adverse events (AEs) will include all AEs that started or worsened during the on-treatment period. When specified, some AEs summaries will include all AEs occurring during the overall safety period.

The number (and percentage) of subjects with treatment emergent adverse events will be summarized by primary system organ class (SOC), preferred term (PT) and maximum severity. A subject with multiple occurrences of an AE will be counted only once in the respective AE category. A subject with multiple CTCAE grades for the same PT will be summarized under the maximum CTCAE grade recorded for the event. AEs will be assessed according to the Common Terminology Criteria for Adverse Events (CTCAE) version 5.0.

In the AE summaries, the primary SOC will be presented alphabetically, and the PT will be sorted within primary SOC in descending frequency. The sort order for the PT will be based on their frequency in the “overall” column (combining the two dose levels of MBG453). The summaries will show ‘All grades’ (including AEs with missing grade) and ‘Grades  $\geq$  3’.

The following adverse event summaries will be produced selecting all or a subset of AEs depending on seriousness, relationship to study treatment, outcome or action taken:

- AEs (by SOC and by PT) and separately those considered related to study treatment
- SAEs and separately those considered related to study treatment
- SAEs with number of occurrences (an occurrence is defined as  $>1$  day between start and prior end date of record of same PT)
- Non-SAEs
- SAEs with fatal outcome and separately those considered related to study treatment
- AEs leading to permanent study treatment discontinuation by study treatment component (AEs leading to MBG453 permanent discontinuation, AEs leading to azacitidine permanent discontinuation, AEs leading to venetoclax permanent discontinuation and AEs leading to permanent discontinuation of any of the 3 study treatment components)
- AEs leading to dose adjustment/interruption
- AEs requiring additional therapy
- COVID-19 related adverse events by MedDRA COVID-19 (SMQ) terms.

In addition, all AEs and SAE by SOC and PT will be also provided on the overall safety period. All reported AEs will be listed and those that started during the pre-treatment, on-treatment and post-treatment period will be flagged.

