#### **Date of last administration of study treatment (combination)**

The date of last administration of study treatment (or start date of study treatment) is defined as the last date when the last non-zero dose of any last component of the study treatment (MBG453, azacitidine or venetoclax) is administered.

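### The overall safety period is tied to MBG453 alone, so it can end before the on-treatment period and has no end date for subjects never given MBG453

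*SAP*

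**What the plan says.** SAP 2.7 Safety analyses defines two windows that matter here.

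- The on-treatment window: "On-treatment period: from date of first administration of study treatment to 30 days after date of last administration of study treatment". SAP 5.1 defines the last administration of the combination as "the last date when the last non-zero dose of any last component of the study treatment (MBG453, azacitidine or venetoclax) is administered", so this window follows whichever drug is given last.
- The overall window: "An overall safety period will be defined from date of first administration of study treatment to 150 days after the last dose of MBG453". Its start follows any component; its end follows MBG453 only. Protocol 12.5.2 carries the same definition.

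SAP 2.7.1 bases the main AE summaries on the on-treatment period and then adds that "all AEs and SAE by SOC and PT will be also provided on the overall safety period".

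The protocol's rule for following patients has two limbs. Section 9.1.1.1 requires follow-up for "150 days after the last dose of MBG453 or 30 days after the last dose of azacitidine or venetoclax whichever is longer". Sections 6.5.4, 10.1.1 and 10.1.3 also pair the 150-day and 30-day limits on a later-of basis.

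Protocol sections 3 and 6.5.3 allow a patient who cannot tolerate one or two of the drugs to stay on the remainder.

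The Safety Set equals the FAS, and FAS membership requires only "at least one dose of MBG453 or at least one dose of azacitidine or at least one dose of venetoclax".

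**The concern.** A period called overall should contain the on-treatment period. As defined, it does not always do so, because one window is anchored to a single drug and the other to all three. A subject who stops MBG453 and stays on venetoclax for many months can have an event that counts as treatment-emergent in the main tables yet is missing from the overall-period tables. Overall counts could then be lower than on-treatment counts for the same term, which a reader of the final CSR would have no way to explain.

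There is also a gap in the definition. MBG453 is first given on Day 8, while azacitidine and venetoclax start on Day 1. A subject can therefore enter the Safety Set and leave before any MBG453. The SAP foresees this for the Dose-Determining Set ("A subject who leaves the study before receiving any dose of MBG453 will not be included in the DDS") but gives no end date for such a subject's overall safety period.

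**Working it through.** **Inputs**

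- End of overall period: last MBG453 dose + 150 days (SAP 2.7; protocol 12.5.2).
- End of on-treatment period: last dose of any component + 30 days (SAP 2.7 with SAP 5.1).
- MBG453 on Day 8 of a 28-day cycle; venetoclax daily through Day 28 (protocol 6.1.1).

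**Formula.** Let *gap* be the days from the last MBG453 dose to the last dose of any component, and count from the last MBG453 dose. The on-treatment period ends at gap + 30 and the overall period at 150. The overall period ends first when gap + 30 > 150, that is, gap > 120.

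On-treatment days outside the overall period = max(0, gap + 30 − 150) = max(0, gap − 120).

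| Gap (days) | On-treatment ends (day) | Overall ends (day) | On-treatment days left out |
|---|---|---|---|
| 120 | 150 | 150 | 0 |
| 121 | 151 | 150 | 1 |
| 132 | 162 | 150 | 12 |
| 168 (6 × 28) | 198 | 150 | 48 |
| 336 (12 × 28) | 366 | 150 | 216 |

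**On scheduled timing.** If MBG453 is last given on Day 8 of one cycle and venetoclax then continues to Day 28 of the *n*th further full cycle, gap = (28 − 8) + 28*n*.

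- *n* = 3: 20 + 84 = 104 days; nothing is left out.
- *n* = 4: 20 + 112 = 132 days; 132 − 120 = 12 days are left out.

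On this timing, the loss begins with the fourth full cycle without MBG453.

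**When a table count changes.** SAP 2.7.1 counts a subject once per AE category. A count therefore falls only if the subject's first event in that SOC or PT is in the days left out. For the Grade ≥ 3 column, what matters is the first event of that severity.

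**Subjects never given MBG453.** Last MBG453 dose + 150 cannot be computed, and neither document supplies a substitute date.

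**With a later-of rule.** The end becomes max(150, gap + 30). For any gap this is at least gap + 30, so no on-treatment day is left out.

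**The case against.** The strongest reply is that little depends on these tables. The main AE summaries and the AESIs use the on-treatment period, all deaths are summarised, and SAP 2.7.1 lists every reported AE. The overall-period tables are an addition, so no event disappears from the report. That stands, and it limits the importance of the point.

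A second reply is that the window is meant to be specific to MBG453. MBG453 is the investigational drug, and SAP 2.8.3 drops immunogenicity samples taken more than 150 days after its last dose. This does not hold up. The period starts at the first dose of any component, not of MBG453, and its tables cover all AEs. Nor would such a purpose supply an end date for subjects who never received the drug.

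Third, the case may be rare or absent. The one planned route to dropping drugs, after CR and at least 18 cycles, stops azacitidine and venetoclax and keeps MBG453. Some toxicities end all study treatment. It is fair that the frequency is unknown. However, Table 6-5 of the protocol also contains discontinuations of MBG453 alone, and no fixed number of cycles caps the other drugs.

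Fourth, tables on different windows are expected to differ. They are, but not with the overall window giving the smaller count.

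Finally, AE collection narrows after new antineoplastic therapy, and a protocol amendment would be heavy for a supplementary table. The first part does not affect the remedy, because the only days it adds for subjects given MBG453 are already on-treatment days. The second part is reasonable and is reflected in the remedy.

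**Conclusion.** The concern holds. Under the definition as written, the overall period ends before the on-treatment period whenever azacitidine or venetoclax continues more than 120 days past the last MBG453 dose, and max(0, gap − 120) on-treatment days fall outside it. The threshold follows exactly from the stated rules. The example gaps are illustrations, and the 104- and 132-day figures assume dosing on schedule.

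The effect is confined to the overall-period AE and SAE tables. The number of subjects affected cannot be derived from the documents and may be zero. For subjects never given MBG453 the problem is an undefined date that the programmer would have to settle, not a demonstrated loss of events. The definition should be corrected, but no efficacy result or main safety summary depends on it.

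Protocol 12.5.2 adds one inconsistency: it flags listed AEs as pre-treatment, overall safety period or post-treatment. An event in the days left out fits none of these. The SAP's flags use the on-treatment period and avoid this.

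**What to change.** In SAP 2.7, define the overall safety period as running from the first dose of any study treatment component to the later of:

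- (a) 150 days after the last MBG453 dose; and
- (b) 30 days after the last dose of any study treatment component.

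For subjects who never received MBG453, use (b) alone. The period then always contains the on-treatment period and is in line with the follow-up window in protocol 9.1.1.1.

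The SAP change is one sentence and one date derivation, with no new data. Protocol 12.5.2 should ideally carry the same sentence. Protocol 14.1 requires a written, approved amendment for that, which may be impractical now that the study is being terminated. In that case the SAP edit is enough, with the departure recorded in SAP section 4, which currently reports no changes to the protocol-specified analyses.

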### **2.7.1 Adverse events (AEs)**

Summary tables for adverse events (AEs) will include all AEs that started or worsened during the on-treatment period. When specified, some AEs summaries will include all AEs occurring during the overall safety period.

The number (and percentage) of subjects with treatment emergent adverse events will be summarized by primary system organ class (SOC), preferred term (PT) and maximum severity. A subject with multiple occurrences of an AE will be counted only once in the respective AE category. A subject with multiple CTCAE grades for the same PT will be summarized under the maximum CTCAE grade recorded for the event. AEs will be assessed according to the Common Terminology Criteria for Adverse Events (CTCAE) version 5.0.

In the AE summaries, the primary SOC will be presented alphabetically, and the PT will be sorted within primary SOC in descending frequency. The sort order for the PT will be based on their frequency in the “overall” column (combining the two dose levels of MBG453). The summaries will show ‘All grades’ (including AEs with missing grade) and ‘Grades  $\geq$  3’.

The following adverse event summaries will be produced selecting all or a subset of AEs depending on seriousness, relationship to study treatment, outcome or action taken:

- AEs (by SOC and by PT) and separately those considered related to study treatment
- SAEs and separately those considered related to study treatment
- SAEs with number of occurrences (an occurrence is defined as  $>1$  day between start and prior end date of record of same PT)
- Non-SAEs
- SAEs with fatal outcome and separately those considered related to study treatment
- AEs leading to permanent study treatment discontinuation by study treatment component (AEs leading to MBG453 permanent discontinuation, AEs leading to azacitidine permanent discontinuation, AEs leading to venetoclax permanent discontinuation and AEs leading to permanent discontinuation of any of the 3 study treatment components)
- AEs leading to dose adjustment/interruption
- AEs requiring additional therapy
- COVID-19 related adverse events by MedDRA COVID-19 (SMQ) terms.

In addition, all AEs and SAE by SOC and PT will be also provided on the overall safety period. All reported AEs will be listed and those that started during the pre-treatment, on-treatment and post-treatment period will be flagged.

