If the event worsens the event should be reported a second time in the CRF noting the start date when the event worsens in toxicity. For grade 3 and 4 adverse events only, if improvement to a lower grade is determined a new entry for this event should be reported in the CRF noting the start date when the event improved from having been Grade 3 or Grade 4.

Conditions that were already present at the time of informed consent should be recorded in medical history of the subject.

Adverse event monitoring should be continued for at least:

- 150 days after the last administration of MBG453, or 30 days after the last administration of azacitidine, or 30 days after the last administration of venetoclax, whichever is later.
OR
- until the start of a new post treatment antineoplastic medication if sooner than the 150 days mentioned above. If a patient starts post treatment antineoplastic medication, then only adverse events suspected to be related to study treatment should be collected, up to 150 days after discontinuation of MBG453.
- until the EOT visit for patients continuing on MBG453 through an alternative setting (e.g. managed access program or a roll-over study) after the end of the study.

Adverse events (including lab abnormalities that constitute AEs) should be described using a diagnosis whenever possible, rather than individual underlying signs and symptoms. When a clear diagnosis cannot be identified, each sign or symptom should be reported as separate adverse event.

Once an adverse event is detected, it must be followed until its resolution or until it is judged to be permanent (e.g. continuing at the end of the study), and assessment must be made at each visit (or more frequently, if necessary) of any changes in severity, the suspected relationship to the interventions required to treat it, and the outcome.

Adverse events separate from the progression of malignancy (i.e. deep vein thrombosis at the time of progression or hemoptysis concurrent with finding of disease progression) will be reported as per usual guidelines used for such events with proper attribution regarding relatedness to the drug

Information about adverse drug reactions for the investigational drug can be found in the Investigator's Brochure (IB).

Abnormal laboratory values or test results constitute adverse events only if they fulfill at least one of the following criteria:

- they induce clinical signs or symptoms
- they are considered clinically significant

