12.5.2 Safety endpoints

Safety analyses will be summarized for the safety set and by dose level of MBG453.

Safety summaries (tables, figures) include only data from the on-treatment period with the exception of baseline data which will also be summarized where appropriate (e.g. change from baseline summaries). In addition, a separate summary for death including on treatment and post treatment deaths will be provided. In particular, summary tables for adverse events (AEs) will summarize only on-treatment events, with a start date during the on-treatment period (treatment-emergent AEs).

The overall observation period will be divided into three mutually exclusive segments:

1. Pre-treatment period: from day of subject's informed consent to the day before first administration of study treatment
2. On-treatment period: from date of first administration of study treatment to 30 days after date of last administration of study treatment
3. Post-treatment period: any observation starting at day 31 after last administration of study treatment

An overall safety period will be defined from date of first administration of study treatment to 150 days after the last dose of MBG453.

Adverse events

Summary tables for adverse events (AEs) will include only AEs that started or worsened during the on-treatment period. The number (and percentage) of subjects with treatment emergent adverse events will be summarized by primary system organ class, preferred term and maximum severity.

Separate summaries will be provided for study medication related adverse events, death, serious adverse events, other significant adverse events leading to discontinuation, and adverse events leading to dose adjustment.

Serious adverse events and non-serious adverse events will be tabulated. All deaths (on-treatment and post-treatment) will be summarized.

In addition, all AEs and SAEs which started during the overall safety period will be summarized. All reported AEs will be listed and those that started during the pre-treatment, overall safety period and post-treatment period will be flagged.

Vital signs

All vital signs abnormalities will be summarized by visit.

12-lead ECG

HR and QTcF will be obtained from 12-lead ECGs for each subject at screening and during the study. ECG data will be read and interpreted centrally.

Categorical analysis of QTcF interval and HR data will be based on the summary of number of subjects meeting or exceeding predefined limits.

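### Once a subject starts new antineoplastic therapy only suspected-related AEs are collected, but the all-causality AE and SAE tables in SAP 2.7.1 neither stop at that date nor separate related events

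*SAP*

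**What the plan says.** **Collection.** Protocol 9.1.1.1 sets the default: "All patients must be followed for safety for 150 days after the last dose of MBG453", or 30 days after the last azacitidine or venetoclax if that is longer. It then makes an exception for subjects who begin new antineoplastic medication within that time: "thereafter only suspected AEs and suspected SAEs will continue to be collected up to the end of the safety follow-up period". Protocol 10.1.1 repeats the exception for AEs: "then only adverse events suspected to be related to study treatment should be collected, up to 150 days after discontinuation of MBG453". Protocol 10.1.3 does so for SAEs, and footnote 4 of Table 8-1 agrees. Protocol 10.1.1 also ends AE monitoring "until the EOT visit for patients continuing on MBG453 through an alternative setting".

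**Analysis.** SAP 2.7 defines two overlapping windows:
- First window: "On-treatment period: from date of first administration of study treatment to 30 days after date of last administration of study treatment"
- Second window: "An overall safety period will be defined from date of first administration of study treatment to 150 days after the last dose of MBG453"

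The main AE tables use the first window. For the second, SAP 2.7.1 adds: "In addition, all AEs and SAE by SOC and PT will be also provided on the overall safety period". Protocol 12.5.2 plans the same: "In addition, all AEs and SAEs which started during the overall safety period will be summarized".

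Under SAP 2.1 the denominator is the number of subjects in the relevant population. Under SAP 2.7.1 a subject counts once per AE category. The tables of related events are specified among the on-treatment summaries; none is specified for the overall safety period.

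**The concern.** An all-causality percentage is read as the share of subjects who had the event, whatever its cause, at any time in the stated window. For a subject who switches therapy inside the window, an unrelated event after the switch is not collected, but the subject stays in the denominator. The table heading does not change, and nothing tells the reader how many subjects are affected.

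The SAP treats the same event explicitly elsewhere. CR counts only assessments before new antineoplastic therapy (SAP 2.5.3), and duration of response and EFS are censored at it (SAP 2.6.1). The safety section has no matching rule. Switching is also foreseeable: Protocol 6.1.5 and 6.1.5.1 stop study treatment at progression or relapse, and SAP 2.4.2 plans a summary of later antineoplastic medication.

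At stake is how the overall-period tables compare with the on-treatment tables. A small increase could be taken as few late events when part of it reflects collection that had narrowed.

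**Working it through.** The plan states no AE rate and no switching rate, so there is no figure to reproduce. The check is a comparison of rules, then an illustration of size.

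**1. Rules side by side**

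| Subject's situation | What is collected | What SAP 2.7.1 tabulates |
|---|---|---|
| No new therapy within 150 days of last MBG453 | All AEs/SAEs | All AEs/SAEs |
| New therapy starts within the window | All before it, suspected-related only after it | All AEs/SAEs, no cut |
| Continues MBG453 elsewhere after the study | All to EOT, then none | All AEs/SAEs, subject stays in denominator |

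Only the second row mixes two collection rules. The third is the end of follow-up.

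**2. Extra time in the overall safety period.** If azacitidine or venetoclax continues k days after the last MBG453 dose, the days added beyond the on-treatment period are 150 − 30 − k, with a floor of zero: 120 for k = 0, 100 for k = 20, 60 for k = 60, and none for k = 120 or more.

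**3. Shortfall for one preferred term.** The table is cumulative from first dose and counts a subject once, so an event is missed only in a subject not already counted. The shortfall in the proportion of subjects is

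(1 − p) × q × f × g × u

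- p: share already counted on treatment
- q: share of the rest whose first onset falls after the on-treatment period
- f: share starting new therapy in the window
- g: share of those onsets that fall after the start of new therapy
- u: share of those judged unrelated

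All five are assumptions. The 85 subjects at 800 mg come from SAP section 1. The model leaves out any loss inside the 30-day on-treatment tail.

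Moderate case, q = 0.15, f = 0.3, g = 0.6, u = 0.8:

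| p | Calculation | Points | Subjects of 85 |
|---|---|---|---|
| 5% | 0.95 × 0.15 × 0.3 × 0.6 × 0.8 | 2.05 | 1.7 |
| 50% | 0.50 × 0.15 × 0.3 × 0.6 × 0.8 | 1.08 | 0.9 |
| 90% | 0.10 × 0.15 × 0.3 × 0.6 × 0.8 | 0.22 | 0.2 |

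With f = 0 the shortfall is zero. With every input at the top of its assumed range (q = 0.30, f = 0.6, g = 0.8, u = 0.9) and p = 5%, it is 0.95 × 0.30 × 0.6 × 0.8 × 0.9 = 12.3 points, or 10.5 subjects.

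**4. Share of first post-treatment onsets captured**, 1 − f × g × u, for g from 0.3 to 0.8 and u from 0.5 to 0.9: 1.00 at f = 0, 0.93 to 0.99 at f = 0.1, 0.78 to 0.96 at f = 0.3, and 0.57 to 0.91 at f = 0.6.

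Measured against all-cause incidence regardless of later therapy, the error is zero or downward. Counts of related events are not affected by the new-therapy rule.

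**The case against.** The best defence is that the planned counts match a sensible target: every event before new therapy, and only suspected events after it. That avoids charging the next regimen's toxicity to MBG453. The collection rule is stated in four places in the protocol, and the tables concerned are supplementary and descriptive. This largely stands. What it does not answer is that the SAP never states this target, labels the tables as all AEs and SAEs, and shows no count of affected subjects.

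The objection also disposes of several stronger readings that a reader might infer:

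- **That recording turns related-only for everyone at some later stage.** It does so only for subjects who start new antineoplastic therapy; the rest keep full collection.
- **That the SAP reports post-treatment AE percentages which must be too low.** It plans no such table. The overall-period table is cumulative from first dose, and post-treatment AEs are only flagged in a listing.
- **That these tables are the only evidence on late toxicity.** SAP 2.7.2 summarises all deaths, including post-treatment deaths, all reported AEs are listed, and related SAEs are still gathered during survival follow-up (Protocol 9.1.1.3).
- **That lost person-time measures the error.** It does not, because each subject counts once per term from first dose.
- **That subjects continuing MBG453 elsewhere are a second case of mixing.** Nothing is collected for them after EOT, so a cut there would remove no events. The documents do not say that anyone took this route.

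**Conclusion.** The point holds in a limited form. In subjects who start new antineoplastic therapy before the overall safety period ends, or within the 30-day on-treatment tail, the all-causality tables combine full and related-only collection without saying so. Late-onset or uncommon preferred terms can be under-counted.

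The size cannot be fixed from the documents. It is zero without switching and about 0.2 to 2 points in the moderate case; 12.3 points needs every input at its extreme. These figures rest on assumed rates of switching, onset and relatedness. Neither primary analysis (CR rate or DLT) is touched. What is at issue is the meaning of a published safety percentage, and the change is cheap enough to make.

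**What to change.** In SAP 2.7 and 2.7.1:

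1. End the all-causality AE and SAE counts, in both the on-treatment and the overall safety period tables, at the earlier of the period end and the day before new antineoplastic therapy, using the same trigger as the protocol's collection rule.
2. Add AE and SAE tables restricted to suspected-related events over the full overall safety period. For subjects who switch, these events are collected throughout.
3. Footnote both sets with the number of subjects whose all-causality collection ended early, separately for new therapy and for EOT in those continuing MBG453 elsewhere.

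The footnote is needed because the cut makes the count well defined but does not recover events that were never collected.

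The cost is SAP wording, one derived date, two extra tables and the footnotes. Start dates of further antineoplastic therapy are already collected (Protocol Table 8-1, SAP Table 5-1), so no new data and no protocol amendment are needed. The small downside is that suspected events after the switch appear only in the related tables, and the cut all-causality percentages can be slightly lower than those now planned.
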